6.7.2.2. Overall Survival

The overall survival (OS) time is measured from the date of first dose to the date of death from any cause. If the patient is alive or lost to follow-up at the time of data analysis, OS data will be censored on the last date the patient is known to be alive. Overall survival will be summarized

and listed for all treated patients. The KM method (Kaplan and Meier 1958) will be used to estimate the OS curve as well as OS rates at 3, 6, 9, 12, and 18 months.

6.7.2.3. Duration of Response

Duration of Response (DoR) is defined only for confirmed responders (patients with a soft tissue BOR of CR or PR). It is measured from the date of first evidence of soft tissue CR or PR to the earliest date of investigator-determined radiographic disease progression (by objective radiographic disease assessment per RECIST 1.1 for soft tissue AND/OR radionuclide bone scan using PCWG3 criteria for bone) or death from any cause, whichever is earlier. It is calculated as date of radiographic progression or death minus date of first soft tissue response evaluation of CR or PR plus 1. The DoR will be censored according to the same rules as rPFS.

Duration of response will be summarized and listed for all treated patients, and a KM analysis of DoR will be performed to estimate the DoR curve. Point estimates and CIs for DoR quartiles and DoR rates will be calculated every 3 months for the first 18 months.

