6.7.2. Secondary Efficacy Analyses

6.7.2.1. Radiographic Progression-Free Survival

The radiographic progression-free survival (rPFS) time is measured from the date of first dose to the earliest date of investigator-determined radiographic disease progression (by objective radiographic disease assessment per RECIST 1.1 for soft tissue AND/OR radionuclide bone scan using PCWG3 criteria for bone) or death from any cause, whichever occurs first. Patients who have neither progressed nor died will be censored at the day of their last radiographic tumor assessment (if available) or date of first dose if no postinitiation (ie, postbaseline) radiographic assessment is available. The detailed censoring rules are described in [Table JPCY.6.1](#).

Radiographic progression-free survival will be summarized and listed for all treated patients. The Kaplan-Meier (KM) method (Kaplan and Meier 1958) will be used to estimate the rPFS curve as well as rPFS rates at 3, 6, 9, and 12 months.

Table JPCY.6.1. rPFS Event/Censoring Scheme

Situation ^a	Event/Censor	Date of Event or Censor
Radiographic disease progression or death	Event	Earliest date of radiographic disease progression or death ^b
No radiographic disease progression and no death	Censored	Date of last adequate radiographic assessment showing no evidence of disease progression or date of first dose (whichever is later) ^c
Unless		
No baseline radiographic tumor assessment available	Censored	Date of first dose
No adequate postbaseline radiographic tumor assessment available and death reported after 2 scan intervals following first dose ^{c,d}	Censored	Date of first dose
New anticancer treatment started and no radiographic disease progression or death within 14 days	Censored	Date of last adequate radiographic assessment showing no evidence of disease progression prior to (start of new therapy +14 days) or date of first dose (whichever is later) ^c
Radiographic disease progression or death documented after 2 or more scan intervals following last adequate radiographic tumor assessment or first dose (whichever is later) ^{c,d}	Censored	Date of last adequate radiographic assessment showing no evidence of disease progression or date of first dose (whichever is later) ^c

Abbreviations: CR = complete response; PD = progressive disease; PR = partial response; rPFS = radiographic progression-free survival; SD = stable disease.

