- a Clinical/symptomatic deterioration that is not radiologically confirmed will not be considered as radiographic disease progression.
- b To be specific, once the radiographic disease progression is observed, especially for confirmed bone progression, the date of disease progression is the date at which initial bone progression (or soft tissue progression, whichever is earlier) is observed, not the date that the bone progression is confirmed by a subsequent assessment.
- c Adequate radiographic tumor assessment refers to an assessment of one of the following:
 - Soft tissue disease with one of the following responses: CR, PR, SD; and adequate bone scan showing no or initial evidence of disease progression.
 - Soft tissue disease with a response of PD.
 - Bone scan showing confirmed disease progression.
 To be specific, “last adequate radiographic assessment showing no evidence of disease progression,” does not include the assessment showing initial/unconfirmed evidence of bone progression. If tumor scans for 1 assessment were performed on multiple days, use the earliest scan date for that visit as the date of assessment.
- d Two scan intervals refer to the time period of next 2 protocol-scheduled radiographic tumor assessments. Time is measured from the last adequate radiographic tumor assessment date. The window of the tumor assessment is also considered. For example, if the last adequate assessment occurs during Cycle 3, the next 2 protocol-mandated assessments are Cycle 5 and Cycle 7, and the window around each assessment is 7 days, then 2 scan intervals will be considered as $2*(28*2 + 7) = 126$ days.

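### Duration of response borrows the rPFS censoring table without moving its anchor from first dose to first response, so a soft-tissue responder without usable bone scans can be censored before his response

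*SAP*

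**What the plan says.** SAP 6.7.2.3 fixes who enters the DoR analysis and when the clock starts. Membership is worded by soft tissue alone: "Duration of Response (DoR) is defined only for confirmed responders (patients with a soft tissue BOR of CR or PR". The duration is given for events: "It is calculated as date of radiographic progression or death minus date of first soft tissue response evaluation of CR or PR plus 1". For everyone else there is one sentence: "The DoR will be censored according to the same rules as rPFS". Protocol 8.1.1 defines DoR without censoring rules, and Protocol 9.4.3 leaves those rules to the SAP.

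The borrowed rules are in SAP 6.7.2.1, Table JPCY.6.1. The general censoring date is "Date of last adequate radiographic assessment showing no evidence of disease progression or date of first dose (whichever is later"). Two rows go straight to first dose. One begins "No baseline radiographic tumor assessment available"; the other begins "No adequate postbaseline radiographic tumor assessment available" and applies to a death more than two scan intervals after first dose. Progression or death found two or more scan intervals after the later of the last adequate assessment and first dose is also censored back to that later date.

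Footnote c defines an adequate visit for a patient who has not progressed as "Soft tissue disease with one of the following responses: CR, PR, SD; and adequate bone scan showing no or initial evidence of disease progression". It adds that a visit with an initial, unconfirmed bone finding cannot supply the progression-free censoring date. Footnote d sets two scan intervals at 126 days.

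**The concern.** The table was built for a clock that starts at first dose. DoR starts later, at first response, and nothing in SAP 6.7.2.3 moves the table's floor or its scan-interval window to that date.

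The second half of the problem is a mismatch of definitions. A CT showing PR without a bone scan can start and confirm a soft-tissue response, yet under footnote c that visit is not adequate. A man can then be in the DoR set with no adequate visit from his response onward, and the borrowed rule looks back to a date before his DoR began.

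At stake are an impossible value in the DoR listing, possible loss of a documented progression from the planned Kaplan-Meier quartiles and 3-monthly rates, and a rule that a programmer would have to make up once the data are in.

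**Working it through.** **Inputs.** First dose is study day 1 (SAP 6.1.2). Scans are due every 8 weeks from Cycle 3 (Protocol 8.1.1), so the nominal days are 57, 113 and 169. The DoR formula is end date minus first CR/PR date plus 1 (SAP 6.7.2.3), extended here to a censoring date.

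**The plan's own figure.** Two scan intervals = 2 × (28 × 2 + 7) = 126 days, which agrees with footnote d.

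**Scans complete and clear.** PR on day 57, confirmed on day 113, last adequate visit day 113: 113 − 57 + 1 = 57 days. First PR on day 113, confirmed on day 169, gives the same: 169 − 113 + 1 = 57. The rule behaves properly here.

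**No adequate visit from first response onward, no event.**
- (a) PR on days 57 and 113, no bone scan at either: censored at first dose, 1 − 57 + 1 = −55 days.
- (b) First PR on day 113, confirmed on day 169, no adequate bone scan at any visit: 1 − 113 + 1 = −111 days.
- (c) SD with clear bone on day 57, then PR on days 113 and 169 without bone scans: censored on day 57, 57 − 113 + 1 = −55 days. First dose is not used.

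**With a progression.** Take case (a) and add soft-tissue progression on day 169. It falls 169 − 1 = 168 days after first dose. Since 168 > 126, the last row of the table censors him at first dose, again −55 days. The observed duration is 169 − 57 + 1 = 113 days, with an event.

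**How general this is.** All combinations of soft-tissue result (PR, SD, not done) and bone scan (clear, initial unconfirmed finding, missing) were enumerated over the three visits. Patterns with at least two PRs were kept, and two successive unconfirmed bone findings were excluded. Of 154 patterns, 48 give a negative censored DoR: 45 end at first dose and 3 at an earlier adequate visit. This counts patterns and is not a probability. Every negative pattern has at least one CT or bone scan missing. With both done at every visit, none is negative.

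**With the table anchored at first response.** The smallest censored DoR in any pattern is 1 day. Case (c) becomes the later of days 57 and 113: 113 − 113 + 1 = 1. In the progression example the window runs from day 57: 169 − 57 = 112 days, within 126, so the progression counts as an event at 113 days.

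**The case against.** The strongest reply is that the general rule takes the later of two dates. A confirmed responder has at least two postbaseline response evaluations, CT and bone scan are both due at the same visits (Protocol 1.3), and one adequate clean visit from response onward is enough to keep the censoring date at or after response. That stands, and it limits the problem to missed or inadequate assessments.

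A second reply is that the man in the example may not be a DoR responder. SAP 6.7 makes nonevaluable or unknown responses nonresponses, and the ORR definition in SAP 6.7.1 requires no concurrent bone progression. Against this, SAP 6.7.2.3 words membership by soft-tissue response only, and no passage says how a missing bone scan is treated. His status is open, which is itself a reason for a sentence.

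A third reply is that first dose is the rPFS time origin, so a sensible programmer would read it as first response for DoR; the DoR formula is also written only for progression or death. That is probably the intention, but the text does not say so.

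Fourth, a negative censored time need not distort the curve. Take five men with assumed times −55 (censored), 113 (event), 120 (event), 170 (censored) and 200 (event). The Kaplan-Meier estimate is 3/4 = 0.75, then 0.75 × 2/3 = 0.50, then 0, whether the first man is entered at −55, 0 or 1 or left out. What changes the curve is the lost progression: as an event at 113 days, the first two steps become 3/5 = 0.60 and 0.60 × 2/3 = 0.40.

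Finally, re-anchoring would leave the man in the progression example with rPFS censored at first dose but a DoR event at 113 days. That follows from each endpoint using its own time origin, and is worth a footnote.

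**Conclusion.** The gap is real but narrow. Read literally, the SAP can censor a confirmed soft-tissue responder before his response (−55 or −111 days in the examples) and can discard a progression seen 112 days after response. It needs the response visits, and any later visits, to be unusable because of missed or inadequate scans. The documents give no basis for a frequency, but it should be uncommon. DoR is a descriptive secondary endpoint, and the primary ORR test is untouched.

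Three stronger readings are not supported:
- A reader might infer that the first-dose fallback alone makes DoR negative. It does not, because the later date is taken. Moreover, case (c) is negative without that fallback, and a man with no baseline assessment is a non-responder under Protocol 9.2.
- A reader might infer that software will drop the man. The documents name no software, and handling of negative times varies.
- A reader might infer that one such man is a fifth of the DoR data, because 5 responders make the study positive. That threshold counts ORR responders, and he may not be among them.

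The figures assume nominal visit days, three postbaseline visits, confirmation by any second PR visit, and the DoR formula applied to censoring dates.

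**What to change.** In SAP 6.7.2.3, state that for DoR each mention of the date of first dose in Table JPCY.6.1 is read as the date of first CR or PR. DoR is then censored no earlier than first response, and two scan intervals are counted from the later of first response and the last adequate assessment.

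Leave footnote c's definition of an adequate assessment as it is. Treating response visits without a bone scan as adequate would relax that definition and is not needed to remove the negative values.

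Add one sentence saying whether a confirmed soft-tissue responder with no bone scan at the response visits is in the DoR set, and whether that matches his status for ORR.

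The cost is two sentences in the SAP. No new data or visits are needed, and the primary analysis does not change if the second sentence only records how ORR already treats such a man.

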6.7.2.4. Disease Control Rate

The disease control rate (DCR) is the percentage of all treated patients with a best response of CR, PR, or stable disease (SD) that do not have concurrent bone disease progression per PCWG3. The DCR will be summarized for all treated patients.

6.7.2.5. Time to Prostate-Specific Antigen Progression

Prostate-specific antigen progression is defined as a $\geq 25\%$ increase and an absolute increase of ≥ 2 ng/mL above the nadir (or baseline value if baseline is the smallest on study), which is confirmed by a second value obtained 3 or more weeks later. Any postbaseline PSA measurements within 12 weeks since baseline will be ignored in determining PSA progression. Time to PSA progression is measured from the date of first dose to the date of first observation of PSA progression. Patients who have not had PSA progression will be censored at the day of their last PSA assessment (if available) or date of first dose if no postinitiation (ie, postbaseline) PSA assessment is available. The detailed censoring rules are described in [Table JPCY.6.2](#).

Time to PSA progression will be summarized and listed for all treated patients. The KM method (Kaplan and Meier 1958) will be used to estimate the time to PSA progression curve as well as landmark survival rates at 3, 6, 9, and 12 months.

Table JPCY.6.2. Time to PSA Progression Event/Censoring Scheme

Situation	Event/Censor	Date of Event or Censor
Confirmed PSA progression	Event	Date of first observation of PSA progression ^a
Not known to have had confirmed PSA progression confirmed	Censored	Date of last PSA assessment showing no evidence of PSA progression or date of first dose (whichever is later) ^b
Unless		
No baseline PSA assessment or no postbaseline PSA assessments available beyond 12 weeks since baseline	Censored	Date of first dose

Abbreviation: PSA = prostate-specific antigen.

- ^a To be specific, for confirmed PSA progression, the date of first observation of PSA progression is the date at which initial PSA progression is observed not the date that the PSA progression is later confirmed by a subsequent assessment.
- ^b To be specific, “last PSA assessment showing no evidence of PSA progression,” does not include the assessment showing initial/unconfirmed evidence of PSA progression.

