### 4.2. Scientific Rationale for Study Design

Patients whose mCRPC has progressed on or after prior NHA(s) and 2 taxane-based chemotherapy regimens represent a population with high unmet medical need.

In the recent CARD study (NCT02485691), treatment with cabazitaxel 25 mg/m^2 (with prednisone 10 mg daily and primary prophylactic granulocyte-colony stimulating factor [G-CSF] at every cycle) offered statistically significant rPFS benefit over anti-androgen therapy (abiraterone or enzalutamide) in participants with mCRPC who were previously treated with docetaxel and progressed within 12 months while receiving the alternative inhibitor (abiraterone or enzalutamide [de Wit et al. 2019]). The median rPFS was 8.0 months in the cabazitaxel group compared to 3.7 months in the anti-androgen group (hazard ratio 0.54; 95% CI, 0.40 to 0.73; p<.001). The principal reasons for the discontinuation of treatment with cabazitaxel or the anti-androgen therapy were disease progression (in 43.7% and 71.0% of the patients, respectively) or an AE (in 19.8% and 8.9% of the patients, respectively). The median OS was 13.6 months in the cabazitaxel group compared to 11.0 months in the anti-androgen group (hazard ratio 0.64; 95% CI, 0.46 to 0.89; p=.008 [de Wit et al. 2019]).

While these results support the use of cabazitaxel over a second NHA in this setting, as yet, there are limited data to guide treatment for mCRPC patients experiencing disease progression after receiving a NHA, docetaxel and cabazitaxel. This represents a high unmet medical need, as there was no standard of care for these patients. Of interest, in CARD, only about half (53.5%) of the patients in the cabazitaxel group received a subsequent anticancer treatment, 23.2% crossed over to receive a second hormonal agent (abiraterone or enzalutamide), 14.7% received palliative radiation, 4.7% received radium-223, 4.7% were enrolled in clinical trials to receive an investigational drug and 1.6% received docetaxel as re-challenge (de Wit et al. 2019).

The single arm, open label design for this study is justified as currently there are limited standard therapies with demonstrated activity for the study population.

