both confirmed and unconfirmed responses may also be reported. Calculation of BOR will be done for each patient in the treated population and will include all response evaluations through the short-term follow-up visit and before the initiation of poststudy-treatment discontinuation therapy.

The primary analysis of the primary endpoint of ORR will be performed approximately 6 months after the last patient enters treatment. In certain circumstances, it may be appropriate to perform the primary analysis earlier (for instance, if all treated patients have experienced objective disease progression). All secondary endpoints will be evaluated at this time. Additional updated analyses of efficacy and safety may be conducted at later times if deemed appropriate by the sponsor.

The ORR will be evaluated against a null hypothesis of 5%. At the time of primary analysis, if 5 or more responders are observed in the planned 40 patients, the study will be considered positive. This is equivalent to a p-value $<.05$ for the exact test of a null hypothesis of an ORR of 5% against an alternative of ORR $>5\%$.

Lilly or its designee will collect and store tumor assessment images, and an independent review of imaging scans may be performed by Lilly or its designee. Analyses of ORR may be repeated using independently reviewed BOR and presented as sensitivity analyses.

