6.7.2.6. Prostate-Specific Antigen Response Rate

The PSA response rate is defined as the proportion of participants with a reduction in PSA level $\geq 50\%$ from baseline, confirmed with a second assessment conducted at least 3 weeks later. The PSA response rate will be listed and summarized for all treated patients.

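### PSA response rate and time to PSA progression are not cut at the start of new anticancer therapy, so a follow-up PSA drawn under the next drug can confirm a response or cancel a rise in a small number of men

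*SAP*

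**What the plan says.** **Imaging endpoints.** SAP 6.7.1 limits BOR, and so ORR: its calculation "will include all response evaluations through the short-term follow-up visit and before the initiation of poststudy-treatment discontinuation therapy". Table JPCY.6.1 gives rPFS a censoring row for "New anticancer treatment started and no radiographic disease progression or death within 14 days". Duration of response inherits that row: "The DoR will be censored according to the same rules as rPFS".

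**PSA endpoints.** The text of SAP 6.7.2.5 reads: "Patients who have not had PSA progression will be censored at the day of their last PSA assessment (if available"). Table JPCY.6.2, which 6.7.2.5 presents as the detailed censoring rules, censors a man without confirmed PSA progression at: "Date of last PSA assessment showing no evidence of PSA progression or date of first dose (whichever is later"). Its only exception covers a missing baseline PSA or no PSA beyond 12 weeks. PSA response in SAP 6.7.2.6 needs a fall of at least 50%, "confirmed with a second assessment conducted at least 3 weeks later", with no condition on therapy. Protocol 8.1.1 defines it the same way. Protocol 9.4.3 sends the censoring rules to the SAP, so the gap is not filled there.

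**Timing.** The Schedule of Activities (Protocol 1.3) draws PSA at baseline, on Day 1 of each 28-day cycle and at Visit 801, but not in long-term follow-up. Visit 801 is 30 ± 7 days after the decision to stop. Protocol 6.5 bars other anticancer therapy only while the man is on abemaciclib. No rule places the Visit 801 PSA before the next therapy. Such an order is written for the optional biopsy (1.3.1) and for imaging at symptomatic progression (7.1).

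**The concern.** The SAP accepts for its imaging endpoints that a result obtained under another drug should not be credited to abemaciclib, but it does not carry this over to the two PSA endpoints. Followed as written, a PSA drawn under the next drug is treated as an abemaciclib result.

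Both are named secondary activity endpoints in a single-arm trial, so no control arm would show the contamination. The only sensitivity analysis in SAP 6.7.3 is central review of imaging, which cannot show it either. For PSA response, the missing limit can only add responders compared with a BOR-type rule. For time to PSA progression, it can turn an event into progression-free follow-up.

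**Working it through.** **1. Figures stated in the plan.** The ORR rule (5 or more responders of 40) reproduces by exact binomial: 4.80% at a true rate of 5% and 73.67% at 15%, against the stated 4.8% and 73.7%. The protocol's exact interval for an observed 0.05 with n = 40 (9.4.6.8) also reproduces: 2/40 gives 0.006 to 0.169. The plan states no power or expected rate for the PSA endpoints.

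**2. Can the Visit 801 PSA serve as the confirming value?** The last on-treatment PSA is on or before the decision to stop. The shortest in-window gap is 30 − 7 = 23 days, and confirmation needs 21. An in-window Visit 801 PSA therefore always qualifies.

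**3. A rise cancelled (invented values, SAP rules).**
- PSA is 60 at baseline and 60 on day 85. On day 113 (Cycle 5 Day 1, a scan visit) it is 90: 90/60 = 1.50 and +30 ng/mL, so the 25% and 2 ng/mL limits are both met, beyond 12 weeks.
- Abemaciclib stops for radiographic progression, the next therapy starts on day 120, and Visit 801 on day 113 + 30 = 143 gives PSA 70: 70/60 = 1.167, below 1.25.
- The rise is unconfirmed and day 143 shows no progression. An event at day 113 becomes censoring at day 143.

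**4. A response confirmed.** Baseline is 100 and PSA first falls to 48 on day 113. The next therapy starts on day 120 and Visit 801 on day 143 gives 45. Both values are at most half of baseline, so this counts as a confirmed response, with the confirming value drawn under another drug.

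**5. Size, PSA response.** One man is 1/40 = 2.5 points. For scale, 2/40 = 5.0% (exact 95% CI 0.6 to 16.9) and 3/40 = 7.5% (1.6 to 20.4). The documents give nothing from which to count such men.

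**6. Size, time to PSA progression, on assumed inputs.** A simulation used median time to stopping of 3.7 months (borrowed from the rPFS of the anti-androgen arm quoted in Protocol 2.2.1), median time to PSA progression of 4 months, 20 to 80% starting the next drug before Visit 801, and 30 to 60% of those falling below threshold.

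| Rule | PSA-progression-free at 6 months |
|---|---|
| As written | 0.48 to 0.50 |
| Plain cut at new therapy | 0.44 to 0.47 |
| Cut, unconfirmed last rise counted as event | 0.41 to 0.47 |

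On average, 0.29 to 1.30 of 40 men had their first rise at the last on-treatment PSA and Visit 801 under a new drug.

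The shift in the table is not mainly cancelled rises. In the 80%/30% setting the plain cut has fewer events (18.2 against 19.0) and still a lower estimate (0.437 against 0.490). That comes from censoring dates: men with no rise who start the next drug early are followed to Visit 801 under the current rule and only to the last on-treatment PSA under the cut. The simulation lets every such Visit 801 value extend follow-up, so it leans towards the high side.

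**The case against.** **Few men are exposed.** PSA is drawn every cycle, and Protocol 7.1 keeps men with PSA-only progression on treatment, so the next Day 1 value will usually do the confirming. This stands, and it is why the point is limited to a first change at the last on-treatment PSA.

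**The effect is not one-directional.** A Visit 801 value that stays high under the next drug confirms a progression. This stands for time to PSA progression. It does not apply to PSA response.

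**A plain cut could do harm.** In step 3, a cut at new therapy leaves the man censored, at day 85 rather than day 143. Had his Visit 801 PSA been 95 (95/60 = 1.58), the current rule would record the event at day 113, while a plain cut would delete it. This stands, and the fix is worded to avoid it.

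**The endpoints are descriptive.** SAP 6.1 calls the analyses mostly descriptive, and trial success depends only on confirmed RECIST responders. This limits the weight of the point but does not justify different attribution rules within one SAP.

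**A stronger reading to avoid.** Protocol 4.2 reports of the cited randomised study that "only about half (53.5%) of the patients in the cabazitaxel group received a subsequent anticancer treatment". A reader might multiply, 0.535 × 40 = 21.4, and infer widespread misclassification. The documents do not support that. The figure covers any later treatment at any time in an earlier-line arm, and it includes 14.7% palliative radiation. The listed non-radiation categories sum to 23.2 + 4.7 + 4.7 + 1.6 = 34.2%. Nothing says how many men start before Visit 801, and an exposed PSA value is not a changed classification.

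**Conclusion.** The gap is real. BOR, rPFS and duration of response are limited at new anticancer therapy; PSA response rate and time to PSA progression are not, and the schedule allows a Visit 801 PSA under the next drug to act as the second value.

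The size is small and not known from the documents. Reclassification needs a first qualifying change at the last on-treatment PSA and new therapy before Visit 801: about 0.3 to 1.3 of 40 men for a first rise, wholly on the assumptions in step 6, and no supportable count for a first fall. Other men who start early without a rise are not reclassified, but their censoring date can move later. Each misclassified responder is worth 2.5 points.

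A reader might also infer that the next drug could produce a whole PSA response. With scheduled samples it cannot: Visit 801 is the only post-treatment PSA, so a first fall there has no later value to confirm it. The ORR and its decision rule are untouched. This is a worthwhile correction to two secondary endpoints, not a threat to the trial's conclusion.

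**What to change.** 1. **SAP 6.7.2.6.** Count only PSA values, including the confirming value, obtained before the start of new anticancer therapy, matching 6.7.1. Cost: a few men lose a confirming value, so the rate may fall slightly.

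2. **Table JPCY.6.2.** State that PSA values after the start of new therapy can neither extend the censoring date nor cancel a rise first seen before it:
   - no rise before new therapy: censor at the last PSA showing no progression on or before its start;
   - rise before new therapy, still above threshold at Visit 801: event at the date of the first rise;
   - rise before new therapy, neither confirmed before it nor sustained at Visit 801: censored in the main analysis, event in a sensitivity analysis.

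   In the simulation this rule treats each man as one of the two cut versions does, so its estimate lies between theirs. Cost: starting new therapy is related to progression, so the added censoring may be informative; the sensitivity analysis addresses only the last group.

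3. **Align text and table in 6.7.2.5.** The text censors at the last PSA assessment; the table censors at the last one without evidence of progression.

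The work is one sentence, a few table rows and one sensitivity analysis. Post-discontinuation therapies are already collected, and the rPFS rule already needs their start dates.
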